5.5 Study Evaluations

Data are collected from participant self-report before, after, and at 6-month follow-up from interventions. Descriptive measures collected at baseline include demographics (age, sex, race/ethnicity, marital status, education) and clinical characteristics (medical comorbidities, medications, psychiatric diagnoses, substance use). Mini-Mental State Examination is collected at screening.

Primary Outcome: The primary outcome is change in mean pain severity scores on the Brief Pain Inventory (BPI) (70) from baseline to post-treatment. The BPI is a short, self-administered questionnaire that was developed for use in cancer patients but is now one of the most widely used tools for assessing a variety of pain conditions in clinical and research settings (71, 72). The BPI contains four items rated 0-10 assessing worst and least pain during the last seven days, as well as average pain and current pain. The mean of these four items is determined to assess mean pain severity. This metric is referred to alternately in the literature as “mean pain severity” and the “pain severity index” (24).

Secondary Outcomes: Consistent with recommendations from IMMPACT (73) and our pilot data, we examine pain interference, physical symptoms (sleep disturbance, fatigue), emotional symptoms (anxiety, depression, PTSD symptoms), purpose and meaning, patient-reported global impression of change, and satisfaction with treatment as secondary outcomes. PROMIS and NIH Toolbox measures are used, where available, because of their long-term potential to improve standardization of patient-reported outcomes (79).

Potential Moderators: Based on previous literature and our pilot work, we examine whether greater baseline anxiety or depression predict greater response to EAET on primary and secondary outcomes post-treatment and at follow-up, and lower baseline anxiety or depression predict greater response to CBT on primary and secondary outcomes post-treatment and at follow-up. We use the same PROMIS measure to evaluate baseline anxiety and depression as used for secondary outcomes.

Potential Mediators: Potential mediators are assessed using standardized assessments which have been validated in the chronic pain population. Emotional approach coping, ambivalence over emotional expression, emotion differentiation, self-conscious affect, anger discomfort, and emotional associations are assessed at baseline, post-treatment, and 6-month follow-up to represent emotion regulation, the proposed distinct mediator for EAET. Pain catastrophizing and coping skills are assessed at baseline, post-treatment, and 6-month follow-up to representing cognitive and behavioral coping, the proposed distinct mediators for CBT. Change on these measures baseline to post-treatment and 6-month-follow-up will be compared to changes in outcomes from baseline to post-treatment and 6-month follow-up. In addition, working alliance, pain beliefs, pain attitudes, and pain control are assessed to mediate response to both treatments. Working alliance will be compared to treatment response at post-treatment and 6-month follow-up. Patients will also be given the opportunity to answer a few open-ended questions at 6-month follow up to assess for mediators that may be worth exploring in future research.

All study variables and their associated measurement instruments are shown in **Table 2**.

Table 2: Study Assessments			Base-line	Post-treat.	6-mo. f/u	Expect. Direct. of Change
Primary Outcome	Variable	Measurement Instrument				
	Cognition	Mini-Mental State Examination	Screening only			
	Pain Severity	Mean of 4 Brief Pain Inventory (BPI) (70) Items:	✓	✓	✓	↓
		Current Pain				
		Average Pain				
		Worst Pain – 7 days				
		Least Pain – 7 days				
Secondary Outcomes	Pain Interference	PROMIS-Pain Interference Short Form (80, 81)	✓	✓	✓	↓
	Pain Behavior	PROMIS-Pain Behavior Short Form (80,	✓	✓	✓	↓
	Depression	PROMIS-Depression Short Form (40)	✓	✓	✓	↓
	Anxiety	PROMIS-Anxiety Short Form (40)	✓	✓	✓	↓
	PTSD Symptoms	PTSD Symptom Scale (82)	✓	✓	✓	↓
	PTSD Symptoms	PCL-5 with LEC-5 and Criterion A (94)	✓	✓	✓	↓
	Purpose and	NIH Toolbox-Purpose and Meaning Short	✓	✓	✓	↑

	Meaning	Form (83)			
	Life Satisfaction	NIH Toolbox-Life Satisfaction Short Form	✓	✓	✓ ↑
	Positive Affect	NIH Toolbox-Positive Affect Short Form	✓	✓	✓ ↑
	Sleep Disturbance	PROMIS-Sleep Disturbance Short Form (84)	✓	✓	✓ ↓
	Fatigue	PROMIS-Fatigue Short Form (85)	✓	✓	✓ ↓
	Global Improvement	Patient Global Impression of Change (PGIC) (86)		✓	✓ ↑
	Patient Satisfaction	Satisfaction with Therapy and Therapist Scale—Revised (74)		✓	
Mediators	Ambivalence	Ambivalence over Emotional Expression Questionnaire (AEQ) (46)	✓	✓	✓ ↓
	Emotional Approach	Emotional Approach Coping Scales (EAC) (77)	✓	✓	✓ ↑
	Emotion Differentiation	PANAS Emotion Differentiation (95)	✓	✓	✓ ↑
	Self-Conscious Affect	Test of Self-Conscious Affect 3 - short version (TOSCA-3) (96)	✓	✓	✓ ↓
	Anger Discomfort	Anger Discomfort Scale (97)	✓	✓	✓ ↓
	Emotional Associations	Property Association Task (98)	✓	✓	✓ ↑
	Catastrophizing	Pain Catastrophizing Scale (PCS) (87)	✓	✓	✓ ↓
	Pain Coping	Coping Strategies Questionnaire (CSQ) (88)	✓	✓	✓ ↑
	Pain Beliefs	Pain Beliefs and Perceptions Inventory (PBAPI)	✓	✓	✓ ↓
	Pain Control	Beliefs in Pain Control Questionnaire (BPCQ)	✓	✓	✓ ↑
	Pain Attitudes	Survey of Pain Attitudes (SOPA)	✓	✓	✓ ↑
	Working Alliance	Working Alliance Inventory (WAI) (89)		✓	
	Future Mediators	Open-Ended Questions			✓ N/A

5.6 Interventions and Interventionists

Interventions:

Emotional Awareness and Exposure Therapy (EAET) includes one individual preparatory session plus 8 weekly group therapy sessions for small groups of 8 Veterans. The conceptual model of EAET is based on 1) neurobiological research indicating the importance of the central nervous system in chronic pain disorders; 2) neurobiological evidence showing structural and functional relationships between emotional brain circuits (e.g., anxiety) and brain circuits dealing with pain; 3) experiential and psychodynamic theories and particularly the relationship between life stress, emotional coping, and symptoms (pain); 4) epidemiological evidence relating trauma/life stress to pain; and 5) research relating alexithymia, emotional expression, and emotional awareness to pain and other somatic disorders. We will use the most updated version of the EAET treatment manual and accompanying patient handouts (26). The sessions include:

- Individual preparatory session. Following screening and consent, each participant receives a psychodiagnostic interview (90) and pain history (26). These components focus on stressful events, how the patient unconsciously avoids emotional experiences,

and how this avoidance is linked to the onset and maintenance of pain and associated symptoms (e.g., depression, anxiety, fatigue).

- Group Session 1: Rationale; Model of Stress, Emotions, and Pain; Identifying Stress-Symptom Connections. The therapist presents the intervention and rationale, including the links between life stress, emotional avoidance, and pain, and the role of altered pain pathways in the central nervous system. The therapist presents the task of therapy, which involves attenuating pain through directly addressing stress and experiencing previously avoided emotions. Home exercises throughout will include increasing activities, reading, and completing worksheets on avoidance, stress, and disclosure of emotions.
- Group Session 2: Triangle Model of Stress and Symptoms; Experiencing and Expressing Anger and Closeness. This session focuses on the Triangle Model, which represents how people function internally, including their emotions, avoidance techniques, and anxiety/symptoms. In-session experiential exercises are introduced to focus on overcoming avoidance techniques and fully experiencing and expressing avoided emotions, starting with anger and emotions related to closeness with others. An avoidance log is introduced for patients to keep track of avoided emotional experiences.
- Group Session 3: Avoidance in Daily Life; Conflicted Relationships; and Experiencing, Expressing, and Releasing 1. Conflicted relationships that lead to emotional avoidance are discussed, and imaginal exercises which focus on experiencing, expressing, and releasing difficult feelings during the session are practiced.
- Group Session 4: Reversing Self-Blame and Guilt with Self-Compassion and Self-Forgiveness; Experiencing, Expressing, and Releasing 2. This session focuses on the difference between healthy guilt when one has done wrong and self-blame which is unhealthy and contributes to symptoms. In session exercises focus on reversing self-blame with assertion and building forgiveness and compassion toward oneself.
- Group Session 5: Forgiving Others or Letting Go; Experiencing, Expressing, and Releasing 3. This session focuses on experiences of being violated, hurt, or neglected and releasing emotions that come from these experiences. Further in-session exercises on experiencing, expressing, and releasing emotions are practiced.
- Group Session 6: Shame, Intimacy, and Private Experiences or Secrets. Shame is defined as a sense of self that is bad and discussed as always unhealthy. Experiential exercises focus on intimacy and sharing secrets of which patients are ashamed.
- Group Session 7: Healthy Communication in Relationships. The two parts of healthy communication, connection to others and assertiveness, are discussed and practiced in session. This is distinguished from the intense emotional expression we have practiced thus far.
- Group Session 8: Review and Planning. The final session reviews all exercises and progress made. Participants describe optimal emotional and interpersonal functioning, which serves as a goal for their continued work, and they develop a written plan for continued exercises to perform to meet that goal.

- Group Sessions 5-6: Cognitive Coping and Distraction (CBT-CP Manual Sessions 8-9). These sessions focus on changing cognitions underlying pain, particularly catastrophizing. Cognitive techniques are taught to help patients recognize relationships among thoughts, feelings, and behaviors and replace maladaptive thoughts with alternative, rational coping thoughts. Relaxation through distraction techniques are also taught.
- Group Session 7: Sleep (CBT-CP Manual Session 10). This session addresses the importance of sleep as it relates to chronic pain. Sleep hygiene will be reviewed with patients, and exercises will be completed to improve sleep hygiene.
- Group Session 8 (CBT-CP Manual Session 11). Review and Planning. This session focuses on planning for maintenance by having each participant develop a written plan that lists coping skills to deal with setbacks.

Interventionists:

Experienced interventionists will be primarily responsible for the administration of both EAET and CBT, in keeping with the primary efficacy aim of this research. [name], will conduct EAET sessions, and [name], will conduct CBT interventions.

As they become available, trainees are recruited to assist the primary interventionists with administration of EAET and CBT. Trainee interventionists are psychologists with at least a master's degree in clinical psychology (licensed psychologists, psychology interns, or psychology residents), psychiatrists or psychiatry residents who have completed at least two years of post-graduate training, licensed marriage and family therapists, or social workers. Each interventionist conducts only one of the two conditions to preserve fidelity by assuring there is no overlap or blending of treatments or allegiance effects.

All interventionists receive a detailed outline of the protocol and participate in exercises, activities and group management skills taught through didactic instruction, taped illustrations from model cases, and role-plays of common scenarios prior to assisting with interventions.

Trainee interventionists shadow and assist the primary interventionists for up to eight sessions before conducting interventions independently. Supervision occurs weekly for trainee interventionists working independently, in which video recordings of sessions are reviewed, and it is verified that the skills and content are being faithfully presented according to protocol. Primary interventionists make ratings of adherence to the protocols to assess trainees. Numerical protocol adherence criteria are developed for each session, with satisfactory adherence defined as $\geq 90\%$ of the maximum possible score on the adherence rating scale. Training is reinitiated when adherence is found to decrease below 90% (91). In addition, independent fidelity monitoring occurs for a randomly selected 25% of all sessions (see section below).

Fidelity Monitoring:

Both EAET and CBT therapy sessions are video recorded for the purposes of fidelity monitoring. Video recording is essential for EAET, given the importance of observing participants' nonverbal behavior for this intervention. An independent fidelity monitor, who is a geriatric psychiatrist with research experience, reviews the video recording of one early and one late session from each course of group EAET or CBT (2 out of every 8 sessions = 25%). In addition, the fidelity monitor reviews 2 out of every 8 = 25% individual psychotherapy sessions for both EAET and CBT. The fidelity monitor completes a standardized checklist to ensure that the session covered targeted topics (based on therapy model) but did not contain non-targeted topics (e.g., CBT concepts during EAET treatment). Participants consent to the production of video recording at the time of informed consent for the study by completing HIPAA authorization, in compliance with IRB policy. Videos are produced on a VA-approved laptop, and video files are immediately transferred to our encrypted VA research server.

5.7 Data Analysis

Statistical Plan:

The experimental design for this study is a 2-group randomized superiority trial, with assessments at baseline, post-treatment (primary endpoint), and 6-month follow-up. The aims correspond to comparisons of the effects of two active treatments to each other (Aim 1), moderation of the interventions (Aim 2), and mediation of the interventions (Aim 3).

Prior to performing the primary analyses, descriptive statistics and graphical summaries are obtained for all outcomes to check for missing data, outliers, and the need for transformations or non-parametric methods.

To assess the success of randomization, continuous baseline covariate statistics will be reported and compared with p-values computed using the t-test or the nonparametric analog (Wilcoxon rank sum test). The p-values for comparing categorical baseline covariates will be computed using chi-square tests or the nonparametric analog (Fisher's exact test). We will compare primary pain and secondary outcomes, demographic (age, race/ethnicity, marital status, education) and clinical (number of medical conditions, presence of psychiatric disorder, presence of substance use, presence of opioid medications) characteristics. While we will not anticipate imbalance in a randomized trial, baseline factors that are clinically and statistically significant and are thought or shown to have a nontrivial effect on the pain change or other outcomes will be considered as adjustment factors. If adjustments are needed, both unadjusted and adjusted results will be reported.

Aim 1: Treatment Group Comparisons: The general linear mixed model (GLMM) will be used to compare BPI mean pain severity changes from baseline and other secondary continuous outcomes between the two groups (EAET, CBT) over time in order to account for correlations induced by repeated measures within subjects and allow for both fixed and time-varying covariates. For ease of interpretation, change from baseline is used as the outcome instead of modeling post-treatment pain with baseline pain as an additional predictor. The GLMM produces consistent estimates when there are missing data if the data are missing at random (MAR). Group, time, and the group x time interaction will be evaluated accounting for correlations via random person effects. Analyses will be carried out via intent to treat (ITT). The primary analyses will use all data.

If an adjusted analysis is needed, we will use logistic regression of treatment group versus the selected covariates to create a propensity score. This score will then be used as an added covariate in the GLMM or will be used to create adjustment strata if the association of pain change with the propensity score is nonlinear or not easily modelled.

Aim 2: Moderation of the Interventions. We hypothesize that patients with higher baseline depression and anxiety will experience greater pain reduction from EAET relative to CBT, whereas those with lower baseline depression and anxiety will benefit more from CBT relative to EAET. To test moderation of condition effects by these baseline characteristics, we will use the PROCESS macro developed by Hayes (92). This approach, which is based on the most current statistical considerations for model testing, involves bootstrapped analyses and estimates of various prespecified models, including tests of both moderators and mediators (92). We will examine depression and anxiety separately to test our hypotheses, but we will also explore, using principal components analysis, whether depression and anxiety should be combined into a composite. Significant interactions will be plotted for post-hoc probing, and high and low values (e.g., ± 1 SD from the sample mean) will be plotted. We also will examine cut-scores on the moderators to classify participants into subgroups that are responsive or amenable to each intervention—an approach that can facilitate later tailoring or treatment matching. For exploratory purposes, we will carry out the same analyses for the secondary outcome measures as well.

Aim 3 (Exploratory): Mediation of the Interventions. This aim pertains to the potential mediating effects of ambivalence over emotional expression and emotional approach coping on the effects of EAET, of pain coping and catastrophizing on CBT, and working alliance on both EAET and CBT. For primary and secondary outcomes at post-treatment, we will test the potential mediators that are assessed concurrently. For the 6-month follow-up evaluation, we will test both the post-treatment and the 6-month follow-up (concurrent) mediators. We will examine the mediators separately, but we also will use multivariate methods (principal component scoring algorithm) to explore whether the potential mediators for each intervention should be combined into composites. We will assess mediation by also using the PROCESS macro developed by Hayes (92, 93).

Sample Size and Power Considerations:

Aim 1: Data from our first two pilot groups showed a mean 1.13-point improvement in BPI mean pain severity under EAET compared to a 0.33-point mean improvement of BPI mean pain severity under CBT, a mean difference of $1.13 - 0.33 = 0.80$ points. Using a sample size of $n = 60$ per group and assuming the same SDs, there is 80% power to confirm mean differences as small as 0.70 points using the usual two-sided $\alpha = 0.05$ significance level. In our pilot, only six of 32 participants were lost to follow-up after

completing baseline assessments and randomization. We estimate at least this dropout rate for the proposed study and possibly up to 25% of participants (based on previous studies, e.g., (16)). We therefore will need to enroll at least $60/0.75 = 80$ participants per group or 160 participants total.

Aim 2: A sample size of $n = 60$ has 80% power ($\alpha=0.05$) for confirming correlations as small as $r = 0.35$ (in absolute value) using the usual $\alpha = 0.05$ significance level. Our pilot data shows that the correlation between anxiety and pain change in the EAET group was $r = -0.40$, and the correlation between anxiety and pain change in the CBT group was $r = 0.53$, both well within this margin. Based on the findings of Burger, et al. (23), we anticipate a possibly larger correlation between depression and reduction in pain than found in our pilot groups. We believe that correlations between pain severity change and depression and anxiety also may be even larger, given the large variation in the pilot sample.

Dropouts:

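### If several covariates are selected for the adjusted Aim 1 analysis, the propensity score gives the same estimate as direct entry but a somewhat too large standard error; direct entry is a minor, nearly free improvement.

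*Combined protocol and SAP*

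**What the plan says.** All of this is in section 5.7 (Data Analysis), under Statistical Plan and Aim 1.

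- **Screening.** Baseline characteristics are compared between arms with p-values: "We will compare primary pain and secondary outcomes, demographic (age, race/ethnicity, marital status, education) and clinical" characteristics, the last being number of medical conditions, psychiatric disorder, substance use and opioid medication.
- **Selection.** Only "baseline factors that are clinically and statistically significant and are thought or shown to have a nontrivial effect on the pain change" (an effect on another outcome also counts) are considered for adjustment. A covariate must therefore be both imbalanced and prognostic.
- **Method.** For an adjusted analysis, "we will use logistic regression of treatment group versus the selected covariates to create a propensity score". In the outcome model the plan gives it one of two roles: "This score will then be used as an added covariate in the GLMM or will be used to create adjustment strata". Stratification is the fallback where pain change is related to the score non-linearly or in a way that is hard to model.
- **Reporting.** If adjustment is made, "both unadjusted and adjusted results will be reported".
- **Primary model.** Baseline pain is not a predictor: "change from baseline is used as the outcome instead of modeling post-treatment pain with baseline pain as an additional predictor".

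The plan claims no gain in precision from adjustment. Its stated purpose is to deal with chance imbalance.

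**The concern.** Allocation is 1:1, so each participant's true propensity is 0.5 and the fitted score only summarises chance differences between the arms. It weights covariates by how well they separate the arms, not by how well they predict pain change. As one covariate in a linear model it removes the imbalance, but it can leave much of the covariates' prognostic variance in the residual. The reported standard error then stays nearer the unadjusted one, although the estimator is as precise as direct adjustment.

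At stake is how the adjusted result reads beside the unadjusted one. An interval that is too wide for its own estimate could suggest that the effect did not survive adjustment, when only the method had changed. There is also an analyst's choice: covariate or strata is decided after looking at how the score relates to the outcome.

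**Working it through.** **1. The plan's own figures.** With 60 analysed per arm and the pilot SDs, the sample-size section states that "there is 80% power to confirm mean differences as small as 0.70 points using the usual two-sided" test at 5%. No SD is given as a number, so it is back-solved: SD = 0.70 × √(60/2) / (1.960 + 0.842) = 1.37. The unadjusted standard error is 1.37 × √(2/60) = 0.250. Enrolment of 60/0.75 = 80 per arm reproduces exactly. The power statement is consistent with this SD but cannot be checked independently.

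**2. The mechanism, with no imbalance filter.** Assume k independent covariates that jointly explain R² of the variance of change. Direct entry removes all of R². A score whose direction is unrelated to prognosis removes on average R²/k. Both lose a little through chance correlation with arm, about k/119 for 120 analysed participants:

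- direct SE ≈ 0.250 × √[(1 − R²)/(1 − k/119)]
- score SE ≈ 0.250 × √[(1 − R²/k)/(1 − k/119)]

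For R² = 0.30, against simulation:

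| k | Direct, formula | Direct, simulated | Score, formula | Score, simulated | Share of gain lost, simulated |
|---|---|---|---|---|---|
| 1 | 0.210 | 0.209 | 0.210 | 0.209 | 0% |
| 2 | 0.211 | 0.210 | 0.232 | 0.232 | 55% |
| 3 | 0.212 | 0.211 | 0.240 | 0.240 | 76% |
| 5 | 0.214 | 0.213 | 0.247 | 0.247 | 93% |

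The two estimates differed by 0.001 to 0.008 points on average, correlated above 0.998 and had the same empirical SD. Reported over empirical SE for the score was about 1.08 to 1.19 at R² = 0.30 (k = 2 to 8). A random-intercept mixed model (k = 3, R² = 0.30) gave 0.250 unadjusted, 0.211 direct and 0.237 with the score.

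**3. How often two or more covariates would be selected.** Table 2 lists 12 primary and secondary measures taken at baseline; with 4 demographic and 4 clinical items there are about 20 tests. If they were independent at 5%:

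- none: 0.95²⁰ = 36%
- exactly one: 20 × 0.05 × 0.95¹⁹ = 38%
- two or more: 26%, or 0.264/0.642 = 41% of trials with at least one (32% to 50% for 15 to 25 tests).

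This counts statistical imbalance only. The plan also requires clinical relevance and prognostic value, so multiple selection should be rarer.

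**4. Two selected covariates, both imbalanced at p < 0.05, R² = 0.20.**

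| Setting | Unadjusted SE | Direct SE | Score SE |
|---|---|---|---|
| Independent, imbalanced in the same prognostic direction | 0.249 | 0.233 | 0.234 |
| Correlated 0.6, equal weights | 0.249 | 0.230 | 0.231 |
| Independent, unequal weights (3:1) | 0.248 | 0.232 | 0.247 |
| Independent, opposite prognostic directions | 0.249 | 0.233 | 0.261 |

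The first two lose 4% and 7% of the gain (3 to 4% and 6 to 13% over all R² and weights run). In the last, the score's standard error exceeds the unadjusted one.

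**5. One multi-level factor.** Race/ethnicity and marital status are candidates and usually have several levels. A four-level factor is three model terms reduced to one score. In one simulation the score SE was 0.243 against 0.225 direct at R² = 0.20, and 0.247 against 0.238 at R² = 0.10, with identical estimates.

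**6. The plan's rule from end to end.** Only covariates imbalanced at p < 0.05 enter.

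- *20 candidates, R² 0.10 to 0.35 spread equally.* Over all triggered adjustments, direct SE was 0.241 to 0.258 and score SE 0.245 to 0.259; power at 0.70 was 77 to 82.5% and 77 to 82%; null rejection was 4.5 to 5.0% for both. A result significant with direct entry but not with the score arose in at most 1% of triggered trials.
- *R² = 0.35 concentrated in 3, 6 or 10 covariates.* Power differed by at most 0.3 points over all triggered trials.
- *Two or more selected.* Differences were about 0.5 to 4 points. The 4-point case needed three strong independent covariates and arose in 0.8% of trials.

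**The case against.** The strongest reply is that the adjustment exists to correct chance imbalance, that the score does so with an estimate almost identical to direct entry, and that any error is conservative, contingent and reported beside the unadjusted result. All of this stands, and it is why the point is minor.

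The candidates also include related symptom scales (depression, anxiety, two PTSD measures, pain interference, pain behavior). Independence is therefore the assumption least favourable to the plan, and correlated covariates lose little.

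Nor do the documents give an R². The only covariate correlations with pain change are the pilot ones for anxiety, −0.40 under EAET and +0.53 under CBT. With equal arms and SDs they average (−0.40 + 0.53)/2 = 0.065, so main-effect adjustment for anxiety alone would gain almost no precision.

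A reader might infer that much of the precision gain is generally thrown away. With four independent covariates and R² = 0.20 to 0.35, type I error falls to 1.9 to 3.4%, and at R² = 0.35 power is 85% against 93%. Those figures require every prognostic covariate to enter the score whether or not it is imbalanced. Section 5.7 admits only covariates that are both imbalanced and prognostic, so the documents do not support that reading.

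The reply does not show any advantage of the score. With about 120 analysed participants and a few covariates, no dimension problem calls for one.

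**Conclusion.** The point holds in limited form. When an adjusted analysis is triggered and two or more covariates that are not strongly correlated are selected, or possibly one multi-level factor, the model-based standard error from the propensity score is somewhat too large for its estimate. Exceptions are one continuous or binary covariate (no loss) and covariates that are strongly correlated or imbalanced in the same prognostic direction (little loss).

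Under the plan's selection rule the average cost is well under 1 point of power across triggered adjustments, and about 0.5 to 4 points when two or more covariates are selected. Type I error is not inflated, and the primary unadjusted test and the sample size are untouched.

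These sizes rest on 60 analysed per arm, the back-solved SD of 1.37, and assumed covariate number, R² and correlation. That the two estimates agree does not depend on the exact values; the size of the loss does.

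**What to change.** In section 5.7, replace the paragraph on the propensity score with wording such as:

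> Selected baseline covariates are entered directly as fixed effects in the GLMM. Continuous covariates stay on their continuous scale, with a quadratic or spline term where the relation to change is clearly non-linear.

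Delete the propensity score and the adjustment strata, and with them the choice between the two that depends on the outcome.

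If baseline pain is itself selected, direct entry in a change-score model gives the same treatment coefficient as modelling post-treatment pain with baseline pain as a predictor, so the interpretation as a difference in change is kept.

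The cost is analysis-plan wording and one degree of freedom per model term (three for a four-level factor). No data collection or sample size changes.
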